4.10.4 CSSA

Descriptive statistics (n, mean, SD, median, minimum, maximum) for absolute values and changes from baseline will be presented for each CSSA item and the total score by treatment group at visit 4, visit 5 and if data is available Post 1 week of EOS. Only absolute values will be presented for Questions 4 and 5.

All individual CSSA data will be listed as well.

4.10.5 Prospective Suicidality Assessment

Descriptive statistics (n, mean, SD, median, minimum, maximum) for absolute values and changes from baseline will be presented by study visit and treatment group.

A summary of number and percentage of subjects with a score of <3 and ≥ 3 on prospective suicidality assessment will be displayed in a frequency table by study visit and treatment group.

A listing of patients by treatment arm with a shift of score from <3 to ≥ 3 on prospective suicidality assessment will be displayed.

4.10.6 Safety Monitoring

Safety monitoring will be guided by the established safety profiles of atomoxetine and oxybutynin, and by Phase 1 safety data for the combination. Safety assessments will include physical examinations, measurement of vital signs, monitoring and recording of AEs, SAEs, and pregnancies, suicidality assessment, recording of study or treatment discontinuations, measurement of ECGs, clinical laboratory evaluations, and memory testing. Effects on OSA and sleep parameters (e.g., sleep time and sleep stages) will also be monitored by PSG.

Adverse events of special interest include effects on urine outflow, as both atomoxetine and oxybutynin are associated with urinary retention. Effects of atomoxetine on heart rate and blood pressure are expected to be modest and will also be monitored. Participants with serious cardiac abnormalities will be excluded from the study. Suicidal ideation in children and adolescents is a boxed warning for atomoxetine; however, analysis in adult patients, the target population for the proposed OSA study, did not reveal an increased risk of suicidal ideation or behavior in association with atomoxetine. Safety monitoring in the dose-finding study will use an appropriate questionnaire to monitor for the potential emergence of suicidal ideation or behavior.

Daytime sleepiness is both a potential safety outcome and efficacy outcome in OSA. Both atomoxetine and oxybutynin are associated with somnolence, and oxybutynin is additionally associated with anticholinergic central nervous system (CNS) effects such as memory difficulty. Safety monitoring will therefore include psychomotor vigilance testing and memory testing.

4.11 Other Analyses

4.11.1 Digit Symbol Substitution Test (DSST) Results:

Descriptive statistics (n, mean, SD, median, minimum, maximum) for absolute values and changes from baseline will be presented for DSST score by treatment group. The participant's DSST score is the number of correct items in 120 seconds, i.e. (the number of items were completed – the number of items were incorrect).

Change from baseline in the DSST Score from baseline to the second PSG visit will be compared between 75/5 dose and placebo group using ANCOVA with treatment group as factor and baseline results as a covariate.

Adjusted means, Standard error (SE) of Adjusted means, 95% confidence intervals, within treatment p-values for each treatment group, treatment group difference, 95% confidence interval of the difference and the between-treatment p-values based on the statistical model described above will also be presented

This analysis will be carried out for following treatment comparison

1. 75/1.5 dose arm vs Placebo arm
2. 25/5 dose arm vs Placebo arm

3. 75/5 dose arm vs. 75/1.5 dose arm
4. 75/5 dose arm vs. 25/5 dose arm
5. 75/1.5 dose arm vs 25/5 dose arm

4.11.2 Delayed Word Recall Test (DWRT) Results

Summary information (the number and percentage of subjects by visit and treatment) will be tabulated for total number word recalled (0-10) and not recalled (0-10).

Change from baseline in the total number of words recalled from baseline to the second PSG visit will be compared between 75/5 dose and placebo group using ANCOVA with treatment group as factor and baseline results as a covariate.

Adjusted means, Standard error (SE) of Adjusted means, 95% confidence intervals, within treatment p-values for each treatment group, treatment group difference, 95% confidence interval of the difference and the between-treatment p-values based on the statistical model described above will also be presented

1. 75/1.5 dose arm vs Placebo arm
2. 25/5 dose arm vs Placebo arm
3. 75/5 dose arm vs. 75/1.5 dose arm
4. 75/5 dose arm vs. 25/5 dose arm
5. 75/1.5 dose arm vs 25/5 dose arm

4.11.3 PSG Parameters

PSG parameters are measured in accordance with the American Academy of Sleep Medicine (AASM) scoring manual (Version 2.4).

Descriptive statistics (n, mean, SD, median, minimum, maximum) for absolute values will be presented for the following PSG parameters by study visits and treatment group. Summary statistics based on change from baseline variable only provided for the key PSG parameter. (details will be provided in the TLFs shell document)

- Periodic limb movements per hour
- Total recording time, Time in Bed, Total Sleep Time, Sleep Onset Latency, REM Latency, Latency to Persistent Sleep, Wake After Persistent Sleep and Sleep Efficiency.
- Spontaneous arousals per hour during sleep, Respiratory arousals per hour of sleep, PLM arousals per hour of sleep, Total number of all arousals per hour.
- Average apnea duration, Central Apneas per hour, Mixed Apneas per hour, Obstructive Apneas per hour, Hypopneas per hour
- Average heart rate during TST, total time in minute that SaO_2 is less than 90% during TST, total time in minute that SaO_2 is less than 80% during TST, minimum oxygen saturation during TST, mean SaO_2 during TST

4.12 Determination of Sample Size

The effect of the drug combination in OSA has been investigated in preliminary academic studies that provide an estimate of effect size in a population similar to the planned Phase 2 study population. Data from a single-night cross-over study showed that a high proportion

of participants, 8/9 (88.9%), with demographic characteristics matched to the planned enrollment criterion of the planned Phase 2 study (baseline AHI ≥ 20 , Body Mass Index [BMI] between 18.5 and 40 kg/m², and age from 25 to 65 years) when treated with a combination of 80 mg atomoxetine and 5 mg oxybutynin achieved a clinically relevant threshold of at least a 50% improvement in AHI score. Using a proposed sample size of n=35 for each of the 4 treatment groups, given 90% power and 2-sided alpha of 0.05, the sample size is powered to detect a difference in proportion of responders between the high-dose group and placebo, assuming a response rate as low as 37% in the high-dose group (compared with the preliminary data that suggests response rate may be as high as 90%) and 5% in the placebo group, estimated based on typical test-retest variability of PSG. Alternatively, if test-retest variability of PSG is higher, resulting in a higher placebo response rate of 10%, the study retains 90% power assuming a response rate in the high-dose group of 46%. Participants that discontinue prior to the second PSG visit will not be replaced and will be considered non-responders.

4.13 Changes in the Conduct of the Study or Planned Analysis

Not applicable.

6 APPENDICES

6.1 Schedule of Assessments

Table 1 Schedule of Assessments

| Procedures | Screening and Baseline PSG ¹ | | Blinded baseline placebo, at-home dosing | Treatment Period | | | Visit 5 EOS ² | Notes |
|--|--|---|---|---|----------------------|---------------------------|-----------------------------|--|
| | Non-PSG Daytime Visit 1 | PSG night and next morning, Visit 2 | | Double-blind study treatment, at-home Dosing | Daytime Visit 3 | Visit 4 PSG Visit | | |
| Trial Day (Visit Window) | -28 to -3 | -7 to -1³ | 1 to 2⁴ | 3 – 11 ± 2⁵ | 6⁶ | 12 ± 2⁷ | 26 ± 4 | |
| Pre-screening | X ⁸ | | | | | | | Determination of basic eligibility for the study |
| Informed consent ⁹ | X | | | | | | | |
| Consent for genetic testing for CYP2D6 | X | | | | | | | |
| Inclusion and exclusion criteria | X | | | | | | | |
| Demography | X | | | | | | | |
| STOP-Bang Questionnaire | X | | | | | | | Only used for participants without a history of diagnosis of OSA or CPAP use |
| Physical exam | X | | | | | | | |
| Medical and surgical history | X | | | | | | | Includes drug and substance usage and psychiatric history |
| Blood sample for CYP2D6 genotype | X | | | | | | | |
| Serum pregnancy test (WOCBP only) | X | | | | | | X | |

PAREXEL International

Apnimed
APN-002 (240495)

Apnimed IND 136752
Statistical Analysis Plan

| Procedures | Screening and Baseline PSG ¹ | | Blinded baseline placebo, at-home dosing | Treatment Period | | | Visit 5 EOS ² | Notes |
|---|--|---|---|---|----------------------|---------------------------|-----------------------------|--|
| | Non-PSG Daytime Visit 1 | PSG night and next morning, Visit 2 | | Double-blind study treatment, at-home Dosing | Daytime Visit 3 | Visit 4 PSG Visit | | |
| Trial Day (Visit Window) | -28 to -3 | -7 to -1³ | 1 to 2⁴ | 3 – 11 ± 2⁵ | 6⁶ | 12 ± 2⁷ | 26 ± 4 | |
| Urine drugs of abuse ¹⁰ testing, ethanol testing | X | | | | | | | |
| Randomization | | X | | | | | | Randomization takes place the morning after PSG testing for participants that qualify |
| Medication distribution to participant, and study instructions and device | | X | | | | | | Prior to discharge morning after PSG |
| QHS self-administration of baseline placebo | | | X | | | | | 2 nights of QHS placebo, at home, all participants; administer ~30 minutes prior to bedtime |
| International Prostate Symptom Scale | X | | | | | | | Male participants only |
| QHS administration of randomized study treatment (combination drug or placebo) | | | | X | | X | | Total of 10 nights: 3 nights low dose (25 mg atomoxetine/ 1.5 mg oxybutynin) followed by 7 nights randomized study treatment for participants randomized to active drug; 10 nights placebo for participants randomized to placebo. |
| “Reminder” telephone call/message | | | | X | | | | Day 10, participants reminded about study procedures and upcoming PSG visit ¹¹ |
| Clinical laboratory assessments (hematology, | X | | | | | X | X | |

PAREXEL International

Apnimed
APN-002 (240495)

Apnimed IND 136752
Statistical Analysis Plan

| Procedures | Screening and Baseline PSG ¹ | | Blinded baseline placebo, at-home dosing | Treatment Period | | | Visit 5 EOS ² | Notes |
|---|--|---|---|---|----------------------|---------------------------|-----------------------------|---|
| | Non-PSG Daytime Visit 1 | PSG night and next morning, Visit 2 | | Double-blind study treatment, at-home Dosing | Daytime Visit 3 | Visit 4 PSG Visit | | |
| Trial Day (Visit Window) | -28 to -3 | -7 to -1³ | 1 to 2⁴ | 3 – 11 ± 2⁵ | 6⁶ | 12 ± 2⁷ | 26 ± 4 | |
| clinical chemistry and urinalysis) | | | | | | | | |
| 12-lead ECG | X | | | | | | X | |
| Vital signs ¹² | X | | | | X | X | X | Visit 4 measure both pre-dose and post-awakening from PSG |
| AE/SAE monitoring | | X | X | X | X | X | X | |
| Study Instruction Reminder | | | | | X | | | |
| Oximeter Battery Change | | | | | X | | | |
| Prior/concomitant medication monitoring | | | | | | X | X | |
| Inpatient Polysomnography | | X | | | | X | | |
| ESS | X | X | | | | X | | Measured to determine eligibility and as efficacy outcome on PSG nights |
| CSSA | X | | | | | X | X ¹³ | Item 17 of the CSSA is used to assess suicidality |
| Patient Global Impression- Severity | | X | | | | X | | Measured evening of baseline PSG and Visit 4 PSG |
| Patient Global Satisfaction with Treatment | | | | | | | X | |
| Home Oximetry | | | X | X | | | | Oximeter used all at-home dosing nights |

PAREXEL International

Apnimed
APN-002 (240495)

Apnimed IND 136752
Statistical Analysis Plan

| Procedures | Screening and Baseline PSG ¹ | | Blinded baseline placebo, at-home dosing | Treatment Period | | | Visit 5 EOS ² | Notes |
|--------------------------|--|---|---|---|--------------------|-------------------------|-----------------------------|---|
| | Non-PSG Daytime Visit 1 | PSG night and next morning, Visit 2 | | Double-blind study treatment, at-home Dosing | Daytime Visit 3 | Visit 4 PSG Visit | | |
| Trial Day (Visit Window) | -28 to -3 | -7 to -1 ³ | 1 to 2 ⁴ | 3 – 11 ± 2 ⁵ | 6 ⁶ | 12 ± 2 ⁷ | 26 ± 4 | |
| Delayed Word Recall Test | | X | | | | X | | Administer at similar time after awakening after each PSG |
| DSST | | X | | | | X | | Administer at similar time after awakening after each PSG |

PAREXEL International

Apnimed
APN-002 (240495)

Apnimed IND 136752
Statistical Analysis Plan

Abbreviations: AE = adverse event; CPAP = continuous positive airway pressure; CSSA = Cocaine Selective Severity Assessment; CYP2D6 = cytochrome P450 2D6; DSST = Digit Symbol Substitution Test; ECG = electrocardiogram; EOS = end of study; ESS = Epworth Sleepiness Scale; HIV = human immunodeficiency virus; ICF = informed consent form; IRB = Institutional Review Board; IRT = Interactive Response Technology; OSA = obstructive sleep apnea; PSG = polysomnography; QHS = 1 dose taken at bedtime; SAE = serious adverse event; STOP-Bang = Snoring, Tiredness, Observed apnea, Blood Pressure-Body mass index, Age, Neck circumference and Gender criteria; WOCBP = women of childbearing potential.

- 1 Following pre-screening, participants who meet basic eligibility requirements will be screened during a visit that includes non- PSG evaluations. Participants who otherwise are eligible will be scheduled for an overnight PSG study.
- 2 If a participant discontinues from the study, all EOS procedures should be performed at the discontinuation visit, within 48 hours of the last study dose.
- 3 Final study eligibility is determined the morning after the PSG exam, based on PSG and non-PSG findings, and enrolled participants are randomized and dispensed the study drug. The first dose of study drug should generally be taken that night; however, at the discretion of the investigator, the first night of study treatment dosing can occur up to 1 week later to accommodate scheduling of the on-drug PSG exam.
- 4 Trial day includes overnight through morning completion of endpoints.
- 5 Daily bedtime dosing (qhs in the protocol synopsis) continues through Visit 4 PSG night, i.e., through PSG visit window; final night of study treatment dosing is PSG night.
- 6 Can occur as late as day as Day 7, if necessary for scheduling.
- 7 Preference is for PSG Visit 4 to be on Day 12, but, if necessary to fit individual participant scheduling, may be \pm 2 days.
- 8 Conducted prior to screening/PSG admission; per IRB-approved pre-screening procedures.
- 9 No trial-related assessment is to be carried out before the participant has signed the ICF. Any participant who provides informed consent will have a screening number assigned by the IRT system.
- 10 Includes amphetamines; barbiturates; benzodiazepines; buprenorphine/metabolite; cannabinoids, cocaine/metabolites; Methylenedioxymethamphetamine; methadone/metabolite; opiates; oxycodone/oxymorphone; phencyclidine; by enzyme-linked immunosorbent assay method; test sample is urine.
- 11 Participants must return to PSG lab with study medication, pulse oximeter and study diary.
- 12 Vital signs include the following: seated blood pressure, pulse, respiratory rate; AE collection refers to spontaneous AEs. Participants who experience systolic blood pressure \geq 160, or diastolic blood pressure \geq 100, or heart rate \geq 120 beats per minute will be further evaluated.
- 13 If there are any responses to individual items at EOS Visit that are more than 4 points worse than baseline exam, CSSA is repeated by telephone at 1 week post EOS Visit.

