|--|---|---|---|---|---|---|-----------------|--|
| Vital signs ¹² | X | | | | X | X | X | Visit 4 measure both pre-dose and post-awakening from PSG |
| AE/SAE monitoring | X | X | X | X | X | X | X | |
| Study Instruction Reminder | | | | | X | | | |
| Oximeter Battery Change | | | | | X | | | |
| Prior/concomitant medication monitoring | | | | | X | X | X | |
| Inpatient Polysomnography | | X | | | | X | | |
| ESS | X | X | | | | X | | Measured at Visit 1 to determine eligibility and as efficacy outcome on PSG nights; measured evening of baseline PSG and Visit 4 PSG |
| CSSA | X | | | | | X | X ¹³ | Item 17 of the CSSA is used to assess suicidality |
| Patient Global Impression-Severity | | X | | | | X | | Measured evening of baseline PSG and Visit 4 PSG |
| Patient Global Satisfaction with Treatment | | | | | | | X | |
| Home Oximetry | | | X | X | | | | Oximeter used all at-home dosing nights |
| Delayed Word Recall Test | | X | | | | X | | Administer at similar time after awakening after each PSG |
| DSST | | X | | | | X | | Administer at similar time after awakening after each PSG |

Abbreviations: AE = adverse event; CPAP = continuous positive airway pressure; CSSA = Cocaine Selective Severity Assessment; CYP2D6 = cytochrome P450 2D6; DSST = Digit Symbol Substitution Test; ECG = electrocardiogram; EOS = end of study; ESS = Epworth Sleepiness Scale; HIV = human immunodeficiency virus; ICF = informed consent form; IRB = Institutional Review Board; IRT = Interactive Response Technology; OSA = obstructive sleep apnea; PSG = polysomnography; QHS = 1 dose taken at bedtime; SAE = serious adverse event; STOP-Bang = Snoring, Tiredness, Observed apnea, Blood Pressure-Body mass index, Age, Neck circumference and Gender criteria; WOCBP = women of childbearing potential.

- 1 Following pre-screening, participants who meet basic eligibility requirements will be screened during a visit that includes non- PSG evaluations. Participants who otherwise are eligible will be scheduled for an overnight PSG study.
- 2 If a participant discontinues from the study, all EOS procedures should be performed at the discontinuation visit, within 48 hours of the last study dose.

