8.1.1 Efficacy Endpoint Scales

- The ESS is a self-administered questionnaire with 8 questions. Respondents are asked to rate, on a 4-point scale (0-3), their usual chances of dozing off or falling asleep while engaged in 8 different activities in recent times. The ESS score (the sum of 8 item scores, 0-3) can range from 0 to 24. The higher the ESS score, the higher that person's average sleep propensity in daily life, or their 'daytime sleepiness'. The questionnaire takes approximately 2 or 3 minutes to answer. The ESS is asked during screening as an enrollment criterion. The ESS is also used as a study efficacy outcome. The ESS is administered the day of the non-PSG screening and approximately the same time of day prior to PSG recordings.

- The Participant Global Impression of Severity (PGI-S) is a global index that may be used to rate the severity of a specific condition, (i.e., it is a single-state scale). The scale consists of a 1-item questionnaire designed to assess the participant's impression of disease severity. The scale is considered to have clinical relevance for the participant because it allows participants to respond based on factors that they judge to be the most important in their health status. The PGI-S is administered at the baseline/screening PSG Visit 2 and at PSG Visit 4. The PGI-S is administered at approximately the same time prior to each PSG recording.
- The Participant Global Satisfaction with Treatment scale consists of a 1-item questionnaire designed to assess the participant's satisfaction with the experimental treatment, considering both safety and efficacy. The scale is administered at the end of the study, at the EOS Visit.

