4.9 Efficacy Evaluation

4.9.1 Analysis and Data Conventions

The high-dose AD036 in this study is atomoxetine 75 mg/ oxybutynin 5 mg, similar to the dose used in initial human studies (atomoxetine 80 mg/oxybutynin 5 mg). To explore the potential efficacy and safety of lower atomoxetine and oxybutynin doses, the following 2 additional dose arms will be studied: atomoxetine 75 mg/oxybutynin 1.5 mg and atomoxetine 25 mg/oxybutynin 5 mg. This Phase 2 clinical study will further examine the efficacy and safety of lower dose AD036 versus placebo.

The primary objective (s) of this study is to assess the efficacy of 3 different fixed doses of AD036 (the combination of atomoxetine and oxybutynin) vs. placebo.

The primary endpoint is the proportion of participants with $\geq 50\%$ reduction in AHI from baseline to the second PSG visit (Visit 4).

The primary comparison of the study is

- ATO 75 mg/OXY 5 mg vs placebo in the proportion of participants with $\geq 50\%$ reduction in AHI from baseline to the second PSG visit (Visit 4).

Primary null hypothesis will be

H_0 : Odds ratio for ATO 75 mg/OXY 5 mg versus placebo in participants with $\geq 50\%$ reduction in AHI from baseline to the second PSG visit (Visit 4) = 1

Primary alternative hypothesis will be

H_1 : Odds ratio for ATO 75 mg/OXY 5 mg versus placebo in participants with $\geq 50\%$ reduction in AHI from baseline to the second PSG visit (Visit 4) $\neq 1$.

The other efficacy comparisons of interest also will be tested using logistic regression similar to primary efficacy hypothesis.

Participants that discontinue prior to the second PSG visit will not be replaced and will be considered non-responders.

When change from baseline is assessed at a post-baseline visit, unless otherwise specified, only patients with both baseline and post-baseline measurements will be included in the analyses. If baseline or post-baseline value is missing for a patient, then the change from baseline will be set to missing.

For all PSG safety and efficacy endpoints the screening PSG night (Visit 2) will serve as the baseline. For additional secondary and tertiary endpoints based on home oximetry, the average of the two baseline nights (Placebo baseline two night) will serve as the baseline.

Unless otherwise stated, if baseline data is missing no derivation will be performed and will be set to missing.

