4.9.1.4 Multiple Comparisons/Multiplicity

Hypothesis tests will be performed in a sequential manner to avoid the need to adjust type I error rates for multiplicity, at a 2-sided 0.05 significance level. The sequential order of hypothesis tests will occur as follows:

- Comparison of the proportion of participants with $\geq 50\%$ improvement in AHI from baseline to the second PSG visit in the 75/5 dose group compared with placebo.
- Percent change AHI, high-dose arm vs. placebo.
- Proportion of participants with $\geq 50\%$ improvement in AHI, measured in the supine sleeping position, from baseline to the second PSG visit in the 75/5 dose group compared with placebo.
- Proportion of participants with $\geq 50\%$ improvement in Oxygen desaturation index from baseline (average of 2 baseline nights) to study treatment nights (average of 6 nights) for the 75/5 dose group compared with placebo.
- Change from baseline in the Epworth Sleepiness Scale (ESS) from baseline to the second PSG visit in the 75/5 dose group compared with placebo.
- Change from baseline in the Participant Global Impression of Severity (PGI-S) from baseline to the second PSG visit in the 75/5 dose group compared with placebo.

- Proportion of participants with $\geq 50\%$ improvement in AHI from baseline to the second PSG visit in the 75/5 dose group compared with the lower treatment dose of 25/5.
- In the case that a statistically significant result for the AHI comparison of dose 75/5 to 25/5 is observed, then the proportion of participants with $\geq 50\%$ improvement in AHI from baseline to the second PSG visit in the 75/5 dose group will be compared with the lower treatment dose of 75/1.5.

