Proportion of patients with $\geq 50\%$ improvement in Oxygen desaturation index from baseline to study treatment nights (average of 6 nights) between 75/5 dose and placebo group will be analyzed using a logistic regression model with the treatment group as factors and baseline Oxygen desaturation index as a covariate.

Estimate of the odds ratio along with associated 95% Wald confidence interval (CI) and two-sided p-value will be presented

Similar analysis will be carried out for the each of following treatment comparison on this efficacy variable

All statistical tests of hypotheses will be two-sided and will employ a level of significance of $\alpha = 0.05$.

1. 75/1.5 dose arm vs Placebo arm
2. 25/5 dose arm vs Placebo arm
3. 75/5 dose arm vs. 75/1.5 dose arm
4. 75/5 dose arm vs. 25/5 dose arm
5. 75/1.5 dose arm vs 25/5 dose arm

Change in the ESS from baseline to the second PSG visit in the 75/5 dose group compared with placebo.

Change from baseline in the ESS at second PSG visit (visit 4) will be compared between 75/5 dose and placebo group using ANCOVA with treatment group as factor and baseline results as a covariate.

Adjusted means, Standard error (SE) of Adjusted means, 95% confidence intervals, within treatment p-values for each treatment group, treatment group difference, 95% confidence interval of the difference and the between-treatment p-values based on the statistical model described above will also be presented

Similar analysis will be carried out for the each of following treatment comparison on this efficacy variable.

All statistical tests of hypotheses will be two-sided and will employ a level of significance of $\alpha = 0.05$.

1. 75/1.5 dose arm vs Placebo arm
2. 25/5 dose arm vs Placebo arm
3. 75/5 dose arm vs. 75/1.5 dose arm
4. 75/5 dose arm vs. 25/5 dose arm
5. 75/1.5 dose arm vs 25/5 dose arm

Change in the PGI-S from baseline to the second PSG visit in the 75/5 dose group compared with placebo.

Change from baseline in the PGI-S at second PSG visit (visit 4) will be compared between 75/5 dose and placebo group using ANCOVA with treatment group as factor and baseline results as a covariate.

Adjusted means, Standard error (SE) of Adjusted means, 95% confidence intervals, within treatment p-values for each treatment group, treatment group difference, 95% confidence interval of the difference and the between-treatment p-values based on the statistical model described above will also be presented

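### ESS is scored twice before randomization, but its ANCOVA adjusts for a single, unnamed baseline; adding the other score is an optional gain of 0–17% in residual variance

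*SAP*

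**What the plan says.** **Collection.** The schedules in Protocol 1.3 and SAP 6.1 mark the ESS at Visit 1, Visit 2 and Visit 4. Protocol 8.1.1 agrees: "The ESS is administered the day of the non-PSG screening and approximately the same time of day prior to PSG recordings". Randomization is on the morning after the Visit 2 PSG, so the first two scores precede both randomization and dosing. The SAP's note on the row reads "Measured to determine eligibility and as efficacy outcome on PSG nights". The amended protocol's note is more explicit about roles: "Measured at Visit 1 to determine eligibility and as efficacy outcome on PSG nights; measured evening of baseline PSG and Visit 4 PSG".

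**Analysis.** SAP 4.9.3 compares the change in ESS at Visit 4 "using ANCOVA with treatment group as factor and baseline results as a covariate". The visit that supplies those baseline results is not given. SAP 4.9.1 has a rule for PSG endpoints ("For all PSG safety and efficacy endpoints the screening PSG night (Visit 2) will serve as the baseline") and one for home oximetry ("the average of the two baseline nights (Placebo baseline two night) will serve as the baseline"). The ESS is a questionnaire and falls squarely under neither. SAP 4.4, in its age calculation, calls Visit 1 the baseline visit.

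**Position.** SAP 4.9.1.4 places "Change from baseline in the Epworth Sleepiness Scale (ESS) from baseline to the second PSG visit in the 75/5 dose group compared with placebo" fifth of eight sequential tests. PGI-S and the two comparisons of 75/5 with the lower doses come after it.

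**Missing data.** Under SAP 4.9.1 a missing baseline makes the change missing. SAP 4.9.1.3 does not impute endpoints other than the responder classification.

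**The concern.** One ESS reading contains measurement error, so a second pre-randomization reading of the same scale can carry further information about the Visit 4 score. The trial collects that reading from everyone and, on the natural reading of the SAP, leaves it out of the model. For home oximetry the SAP already combines two pre-treatment nights.

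The ESS is also a gate. If it fails, PGI-S and both dose comparisons cannot be formally claimed, and dose selection is a stated purpose of the study. The documents justify power only for the primary responder endpoint and give none for the ESS, so inexpensive precision here is worth considering. Separately, leaving the ESS baseline visit unnamed when two candidate scores exist is a small specification gap in a test that belongs to the error-controlled sequence.

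**Working it through.** **1. The plan's own figure.** The only stated power is 90% for the primary endpoint with 35 per arm (Protocol 9.2, SAP 4.12). Two-sided Fisher's exact power by full enumeration is 90.7% for 37% v 5% and 90.6% for 46% v 10%, so the figure reproduces. It says nothing about the ESS.

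**2. Inputs for the ESS.**
- From the documents: 35 per arm, four arms, two-sided 0.05; upper ESS entry limit 18; lower limit 4 in the amended protocol and 8 before it.
- Assumed, because the documents give no figure: mean 11, SD 4.5, ICC 0.6–0.8, true effect 2 points.

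**3. Formula.** Let r be the correlation of Visit 2 with Visit 4, h that of Visit 1 with Visit 2, and c that of Visit 1 with Visit 4. Adding Visit 1 as a second covariate removes a fraction of the residual variance equal to the squared partial correlation:

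reduction = (c − h·r)² / [(1 − h²)(1 − r²)]

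With h = r this becomes (c − r²)² / (1 − r²)².

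**4. Before allowing for entry selection (h = r).**

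| r | c = r | c = r − 0.1 | c = r² (AR(1)) |
|---|---|---|---|
| 0.6 | 14.1% | 4.8% | 0 |
| 0.7 | 17.0% | 4.7% | 0 |
| 0.8 | 19.8% | 2.8% | 0 |

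For example, at r = 0.7:
- c = 0.7: (0.70 − 0.49)² / 0.51² = 0.0441 / 0.2601 = 17.0%.
- c = 0.6: (0.60 − 0.49)² / 0.51² = 0.0121 / 0.2601 = 4.7%.

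**5. After selection on Visit 1.** Entry limits narrow the spread of Visit 1 scores and reduce the gain. The simulation used rounded scores with mean 11 and SD 4.5, and kept participants with Visit 1 ESS of 4–18 or 8–18.

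| How Visit 1 relates to Visit 4 | Reduction in residual variance | Power gain, 2-point effect |
|---|---|---|
| As strongly as Visit 2; Visit 1 and 2 errors independent or half shared | 4–17% | 2–6 points |
| Correlation 0.1 lower than for Visit 2 | 1.9–3.7% | 0.6–1.6 points |
| AR(1) decay | 0 | 0 |

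**6. One case in full (ICC 0.7, lower limit 4, independent errors).** Simulated residual variance is 10.00 with Visit 2 alone and 8.64 with both scores, a reduction of 1 − 8.64/10.00 = 13.6%. The standard error of the difference is √(2 × 10.00/35) = 0.756 or √(2 × 8.64/35) = 0.703. The noncentrality is 2/0.756 = 2.65 or 2/0.703 = 2.85, and power is 74.8% or 80.7%. With half-shared errors, power moves from 73.7% to 76.6%.

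**7. Which row is plausible?** Visit 1 may be as early as Day −28 and Visit 4 is Day 12 ± 2, so they can be about 28 + 12 = 40 days apart. Visit 2 is Day −7 to −1, roughly 13 to 19 days before Day 12. Some loss of correlation for Visit 1 is therefore credible, and the lower rows cannot be set aside.

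**8. Separate covariates or the mean?** If Visit 1 is the weaker predictor, averaging can do harm. At r = 0.8 and c = 0.7, the mean leaves 1 − 0.75²/0.9 = 0.375 of the variance, against 1 − 0.8² = 0.360 for Visit 2 alone, which is 4.2% more. Under AR(1) the mean is 11–18% worse. Two separate covariates avoid this. If Visit 1 added nothing, their cost in the case of step 6 is about 0.3 power points.

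**The case against.** **The planned model is sound.** ANCOVA on the reading closest to randomization is valid, pre-specified and unbiased. The amended schedule gives the two scores different roles, and Visit 2 matches Visit 4 in setting and time of day, whereas Visit 1 is a daytime screening visit. This stands. A reader might infer that the ESS comparison is biased or wrongly specified, and the documents do not support that.

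**The size is not known.** A reader might take 4–17% as a guaranteed gain. It holds only if Visit 1 predicts Visit 4 as well as Visit 2 does, and the visit windows make that doubtful. Former CPAP users weaken it further. Inclusion criterion 2 requires a month without CPAP before the PSG, not before Visit 1, so some Visit 1 scores may be taken during CPAP use or soon after stopping. This stands and brings the lower end of the range to zero.

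**The downstream harm is limited.** A reader might infer that a failed ESS test loses the dose comparisons. It blocks formal claims only: SAP 4.9.2 presents their odds ratios, intervals and p-values regardless, and SAP 4.9.3 says that all comparisons will be carried out. Reaching them formally also requires the tests ranked 2 to 4 and PGI-S to succeed, and that joint probability has not been computed here.

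**Missing Visit 2 scores are hypothetical.** Visit 2 is an attended overnight visit immediately before randomization, and nothing in the documents suggests that scores will be lost. Substituting Visit 1 would also depart from SAP 4.9.1 and 4.9.1.3 unless those sections were amended, and would leave displayed change undefined.

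None of this defeats the covariate change. Both scores precede randomization, so adding Visit 1 cannot bias the between-arm contrast, even though participants were selected on it.

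**Conclusion.** The point holds as an optional efficiency gain together with a small specification gap. It is not an error in the planned analysis. The ESS is collected twice before randomization, the ANCOVA carries one baseline term whose visit is inferred rather than stated, and no efficacy model in the SAP uses the Visit 1 score.

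Under the assumed mean, SD and ICC range, the reduction in residual variance lies between 0 and 17%. Where it falls depends on how well Visit 1 predicts Visit 4, which the documents do not tell us. Confidence is therefore moderate: firm on the facts and on the direction (no bias, negligible cost), weak on the size.

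**What to change.** In SAP 4.9.3 (ESS), before database lock:
- Name Visit 2 as the ESS baseline for calculating and displaying change.
- Fit the ANCOVA with treatment as factor and the Visit 2 and Visit 1 ESS scores as two separate covariates, not their mean.

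A fallback for a missing pre-dose score is optional. If adopted, write it as a stated exception to SAP 4.9.1 and 4.9.1.3 and apply it to the covariate only. Change would remain missing when Visit 2 is missing.

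The cost is a sentence or two in the SAP and one degree of freedom. No new data, visits or participant burden are needed, and the test order is unchanged.
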